## 7.1 Toxicity Management

### Grade 1 or 2

Participants who develop a Grade 1 or 2 AE or toxicity may continue ARVs and TB drugs without alteration of the dosage. Participants experiencing Grade 1 or 2 toxicities will be managed at the discretion of the site investigator.

### Grade 3

If there is compelling evidence that the AE has NOT been caused by the study-provided drugs, dosing may continue at the discretion of the site investigator/clinician. Except as stated in the following sections, participants who develop a Grade 3 AE or toxicity thought to be secondary to study-provided drugs or of unknown etiology may have all of their ARVs and/or TB drugs withheld, at the site investigator's discretion. Investigators are welcome to discuss toxicity management with the A5290 CMC. The participant should be reevaluated weekly if at all possible until the AE returns to Grade  $\leq 2$  or until stabilized and no longer in need of such frequent monitoring, as determined by the site investigator, at which time ART and/or anti-TB treatment may be reintroduced at the discretion of the site investigator or according to standard practice.

### Grade 4

Participants who develop a symptomatic Grade 4 AE or toxicity, not specifically addressed below, will have all medications withheld and should be reevaluated weekly if at all possible until the AE returns to Grade  $\leq 2$  or until stabilized and no longer in need of such frequent monitoring, as determined by the site investigator. However, under certain circumstances the ARV or TB drug thought most likely to be related to the AE may be resumed at the discretion of the site investigator. However, if study-provided ARV or TB drugs are permanently discontinued due to a toxicity not otherwise specified in section 7.2, then the participant should continue to be followed on study, off-study-provided medications and referred to their primary clinician for best available management.

Participants with Grade 4 asymptomatic laboratory abnormalities, not specifically addressed below, may continue ART and anti-TB treatment if the site investigator has compelling evidence that the toxicity is NOT related to the ART or anti-TB treatment, or if benefit of the ART or anti-TB treatment outweighs the potential risk.

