Participants who do not have day  $12 \pm 2$  (after initiation of ART) PK samples will not be replaced. Thus, we will enroll 20 participants in each arm, expecting 18 participants in each arm with evaluable PK data. (However, the accrual period 1 PK and safety interim analysis may lead to proposing additional accrual period 1 participants to assure an adequate PK assessment.)

Accrual will be suspended after the last participant is enrolled into the accrual period 1.

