### PK and Safety Criteria

- For RBT (Arms A and C), equivalence analyses will compare day  $12 \pm 2$  (after initiation of ART) RBT 24-hour AUC and  $C_{max}$  with control data derived from prior PK studies, as determined by whether the 90% confidence intervals of the ratios of the RBT concentrations (when co-administered with LPV/r) relative to daily RBT concentrations in the absence of LPV/r are fully contained within the pre-specified NEB of 67%-150%. RBT concentrations in Arms A and C will be judged acceptable if equivalence is declared according to these PK parameters.
- For LPV in Arm B, the primary PK parameter is the day  $12 \pm 2$  (after initiation of ART)  $C_{min}$  ( $C_{12}$ ), and the acceptable lower limit value is  $\geq 1$  mg/L. LPV concentrations in Arm B will be judged acceptable if no more than three participants have a  $C_{min} < 1$  mg/L.
- No more than three participants in any treatment arm experience a Grade 3 or Grade 4 AE attributable to study-provided medication by 28 days after ART initiation.
- No more than three participants in any treatment arm discontinue study-provided drug(s) for treatment-limiting toxicity or intolerance (such that PK assessments within the day  $12 \pm 2$  (after initiation of ART) window cannot be completed).

The justification behind the RBT PK criterion is given in section 9.4.1. The other three criteria depend on the number of events (i.e., no more than 3). Based on Table 9.2 below, supposing the underlying rate is 10%, with  $X=3$ , there is an 87% chance of the study regimen in a particular arm going forward to accrual period 2.

Table 9.2. Probability (%) of Deciding the Criterion is Acceptable Based on a Range of Underlying Rates

Underlying Rate	Probability of X or Fewer Events in 20 Participants Given the Underlying Toxicity Rate:				
	X=1	X=2	X=3	X=4	X=5
0.05	0.736	0.925	0.984	0.997	0.999
0.10	0.392	0.677	0.867	0.957	0.989
0.15	0.176	0.405	0.648	0.830	0.933
0.20	0.069	0.206	0.411	0.630	0.804
0.25	0.024	0.091	0.225	0.415	0.617

The core team will also examine the LPV concentrations in Arms A and C in order to determine if RBT affects LPV concentrations. Any dose modifications of

LPV in Arms A and C will be the guided by the modifications proposed for Arm B (see Table 5.1 in section 5.1.1).

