
NOTE: Any participants determined to have clearly inadequate RBT concentrations during the accrual period 1 PK evaluation should be monitored closely after dose adjustments for TB outcomes throughout the course of their TB treatment.

After 54-60 accrual period 1 participants have completed 28 days of ART and have drug concentrations available, the core team, together with the SMC, will review the results of the full accrual period 1 interim PK and safety analysis.

If the acceptable PK criteria for RBT and LPV are met, and if three or fewer participants in each treatment arm report  $\geq$  Grade 3 AEs attributed to study-provided drug(s) by 28 days of ART, and if three or fewer participants in each treatment arm discontinue study-provided drug(s) for treatment-limiting toxicity or intolerance (such that PK assessments cannot be completed), then accrual period 2 will open at the planned dose schedules of LPV/r and RBT.

If acceptable PK criteria are not met, or if more than three participants in one or more treatment arms report  $\geq$  Grade 3 AEs attributed to study-provided drug(s) by 28 days of ART, or if more than three participants in one or more treatment arms discontinue study-provided drug(s) for treatment-limiting toxicity or intolerance (such that PK assessments cannot be completed), the SMC, in consultation with the core team, may elect to adjust the doses of RBT and/or LPV/r, as described above for all participants in the affected arm identified with inadequate study-provided drug concentrations. Repeat steady-state (day 12  $\pm$  2 after dose adjustment) drug concentrations will be obtained for only the study arm participants in whom a dose was adjusted. A second accrual period 1 PK and safety interim analysis will be conducted after all accrual period 1 participants undergoing dose adjustment have completed 28 days of dose-adjusted treatment and when day 12  $\pm$  2 post-dose adjustment levels are. This second analysis will include all accrual period 1 participants with available data.

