The core team and SMC will then review the results of the second accrual period 1 interim PK and safety analysis. If acceptable PK criteria are not met, or if more than three participants in one or more treatment arms report  $\geq$  Grade 3 AEs attributed to study-provided drug(s) by 28 days of ART, or if more than three participants in one or more treatment arms discontinue study-provided drug(s) for treatment-limiting toxicity or intolerance (such that PK assessments cannot be completed), then a decision will be made about whether to continue, modify (e.g., add additional participants in the accrual period 1 to assure adequate PK assessment are completed), or halt the treatment arm(s) in question, based on analysis of the nature of the AEs and reasons for study-provided drug discontinuation, and the degree of PK criteria failure. At this second interim review, if three or fewer participants report  $\geq$  Grade 3 AEs attributed to study-provided drug(s), and if three or fewer participants discontinue study-provided drug(s) for treatment-limiting toxicity or intolerance (such that PK assessments cannot be completed), and if acceptable PK criteria are met for at least two of the treatment arms, the SMC, in consultation with the core team, will determine whether accrual period 2 will open.

If, based on the SMC's determination, unacceptable PK and/or safety criteria are met within two treatment arms, then further enrollment into the study may be stopped, and accrual period 1 participants will be managed according to best available local TB and ARV treatment. These participants will be followed off study drug for the remainder of study follow-up (up to 72 weeks).

If the SMC determines that accrual period 2 enrollment should proceed, accrual period 2 participants will then be randomized 1:1:1 to Arm A, B, or C (or with

equal probability to the remaining sample size in the remaining treatment arms) at the doses determined during the dose-finding period in accrual period 1 participants. No individual dose adjustments will be made based on drug concentrations for participants enrolled during the accrual period 2.

Based on this monitoring, if criteria are determined to be unacceptable in any treatment arm before the three accrual period 1 cohorts are fully enrolled, further accrual to the arm in question may be stopped.

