## 9.6 Analyses

### 9.6.1 Accrual Period 1 PK and Safety Interim Analyses

Interim PK and safety analyses will be conducted when the first 10-12 accrual period 1 participants per treatment arm have completed 28 days of ART and day  $12 \pm 2$  (after initiation of ART) drug concentrations are available. These early assessments will try to identify any early trends suggesting lower or higher than expected concentrations of any study-provided drug(s). If early assessments indicate concentrations out of acceptable ranges for more than three participants in a treatment arm or trends related to safety criteria, an early ACTG Study Monitoring Committee (SMC) evaluation will be triggered.

The accrual period 1 PK and safety interim analysis will be conducted when 54-60 accrual period 1 participants have completed 28 days of ART and day  $12 \pm 2$  (after initiation of ART) PK results are available. Study participants who discontinue study follow-up prior to day 28 will have their safety data included in the safety analysis. Furthermore, study participants who are lost-to-follow-up prior to day 28 will be considered failures in the safety analysis. Because these participants will be undergoing treatment for active TB, they will continue on their randomized therapy pending the results of this interim PK and safety analysis, but accrual will be suspended until the final accrual period 1 PK and safety interim analysis has been reviewed by the SMC.

For RBT (Arms A and C), an equivalence approach will be used to compare day  $12 \pm 2$  (after initiation of ART) RBT 24-hour AUC and  $C_{max}$  with control data derived from prior PK studies, as determined by whether the 90% CI of the ratios of the RBT concentrations (when co-administered with LPV/r) relative to daily RBT concentrations in the absence of LPV/r are fully contained within the pre-specified NEB of 67%-150%. RBT concentrations in Arms A and C will be judged acceptable if equivalence is declared according to these PK parameters. (Please note: the control data derived from prior PK studies are described in section 10.3.)

For LPV (Arm B), the primary PK parameter is the  $C_{min}$  (trough or 12-hour post dose concentration), and the acceptable lower limit value is  $\geq 1$  mg/L. LPV/r concentrations in Arm B will be judged acceptable if no more than three participants have a  $C_{min} < 1$  mg/L.

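### The 87% in Protocol 9.5.1 is the chance of meeting one count criterion; an arm must meet three, so at 10% rates it is only an upper limit at the first full review

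*Protocol*

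**What the plan says.** Protocol 9.5.1 (PK and Safety Criteria) lists four criteria. Two are safety counts that apply to every arm: participants with a related Grade 3 or 4 event by 28 days of ART, and participants who discontinue for toxicity or intolerance so that the PK assessment cannot be done. The third is the count of Arm B participants with a lopinavir trough below 1 mg/L. The fourth, for Arms A and C, is equivalence of rifabutin AUC and Cmax to control data. Each count passes with three or fewer.

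The section takes the 10% row of Table 9.2 and concludes that "there is an 87% chance of the study regimen in a particular arm going forward to accrual period 2". The table's own title is "Probability (%) of Deciding the Criterion is Acceptable Based on a Range of Underlying Rates".

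The decision rule for the first full review, later in 9.5.1, joins the PK criteria and both safety counts with 'and', across the arms. Only if all are met, "then accrual period 2 will open at the planned dose schedules of LPV/r and RBT". Otherwise doses may be adjusted and a second review held, where one of the conditions is "if acceptable PK criteria are met for at least two of the treatment arms". Protocol 9.6.1 adds that "study participants who are lost-to-follow-up prior to day 28 will be considered failures in the safety analysis".

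Neither document gives a probability that an arm meets all of its criteria.

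**The concern.** The sentence attaches a one-criterion probability to an arm-level event. A reader would conclude that an arm with 10% event rates misses at the review 13% of the time. Because three criteria must hold together, the chance of a miss is at least that, and it equals 13% only if the criteria always pass and fail together.

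The stake is interpretation. SAP 1.5.1 and 1.5.2 keep the same criteria, and SAP 6 says the report will state whether they were judged acceptable. Anyone weighing a failed arm needs to know how often an arm whose rates are as assumed would fail by chance.

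**Working it through.** **Inputs.** Rate 10%, n = 20, limit 3 (Protocol 9.5.1, Table 9.2). Three criteria per arm (9.5.1). Probability of declaring rifabutin equivalence with 18 per group and the 67%-150% boundary: 93-94% at a true AUC difference of 5%, 90% at 10%, 52% at -20% and 70% at +20% (Table 9.1). PK-evaluable number: 9.4.1 enrols 20 per arm, "expecting 18 participants in each arm with evaluable PK data".

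**Plan's figure reproduced.** P(X ≤ 3 | n = 20, p = 0.10) = 0.867. The other Table 9.2 entries also reproduce to within 0.001. With n = 18 the value is 0.902.

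**Upper limit.** The probability of meeting several criteria cannot exceed the smallest single probability. With the safety counts at n = 20 that is 0.867 for Arm B. It is also 0.867 for Arms A and C as long as rifabutin power is at least that high. At a true 20% difference the limit for Arms A and C drops to 0.52 or 0.70.

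**Lower limit under any dependence.** This is the sum of the probabilities minus 2. Arm B with n = 20 on all counts: 3 × 0.867 − 2 = 0.601. Arms A and C with power 0.90: 2 × 0.867 + 0.90 − 2 = 0.634.

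**Illustration between these limits.** The following assumptions are not in the documents: 10% on every count; PK criterion independent of the safety counts; arms independent; rifabutin power 0.90-0.94. In the nested case every discontinuation is also a counted adverse event and the rates are equal, so the two safety counts together pass with 0.867.

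| | Independent criteria | Discontinuations nested in adverse events |
|---|---|---|
| Arm B, trough count n = 20 | 0.867³ = 0.652 | 0.867² = 0.752 |
| Arm B, trough count n = 18 | 0.867² × 0.902 = 0.678 | 0.867 × 0.902 = 0.782 |
| Arms A and C | 0.867² × (0.90 to 0.94) = 0.677 to 0.707 | 0.867 × (0.90 to 0.94) = 0.780 to 0.815 |
| All three arms | 0.652 × 0.677² to 0.678 × 0.707², about 0.30 to 0.34 | 0.752 × 0.780² to 0.782 × 0.815², about 0.46 to 0.52 |

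The miss rate per arm is thus about 18-25% in the nested case and 29-35% under independence, against the 13% implied by the text.

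**Sensitivity to dependence.** A simulation of Arm B with correlated participant-level events (n = 20 on each count) gave 0.67, 0.70 and 0.76 at latent correlations of 0.3, 0.6 and 0.9. When a low trough was counted only in participants who had not discontinued, the value at 0.9 was 0.80. That is above the table's 0.78, which shows that the table does not bound the answer.

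**The case against.** **A failed criterion does not stop an arm.** This stands. A miss leads to committee discretion, possible dose adjustment and a second review. A reader might infer that the chance of ever reaching accrual period 2 is below 0.867. The documents do not support that: neither 0.867 nor the figures above model the second review. The point is confined to the first full review.

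**It has little practical effect now.** This also stands in part. SAP 1.6 states that accrual period 2 will not open, and no threshold or sample size uses the 87%. A reader might infer that the design or recruitment was compromised; nothing in the documents supports that. The sentence is still untrue as written.

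**The text corrects itself.** The table title refers to a single criterion and the table is right. But the sentence is the only interpretation offered, and it names the arm's regimen.

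**The 0.867 limit depends on n = 20.** True. The review takes place with 54-60 participants, so about 18-20 per arm. If 18 were used for the safety counts as well, a single count would pass with 0.902, and the nested values would be 0.902² = 0.81 for Arm B and 0.902 × (0.90 to 0.94) = 0.81 to 0.85 for Arms A and C. Table 9.2 uses 20, and 9.6.1 keeps safety data from participants who leave early, so 20 is the fair base.

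**The nested case is weakly supported.** Fair. In its favour, Protocol 7.1 says participants with Grade 1 or 2 toxicity "may continue ARVs and TB drugs without alteration of the dosage". Against it, withholding for Grade 3 is discretionary, 7.2.3 holds rifabutin for uveitis without naming a grade, 7.2.5 stops suspect drugs for some Grade 2 rashes, and the criterion includes intolerance. Equal rates with full nesting make the two event sets identical, which is extreme.

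**Section 9.4.1 already says AUC.** It does, and Table 9.1 lists power by true difference. What the power sentence lacks is the difference it assumes and the fact that the criterion also requires Cmax.

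**Conclusion.** The point holds as a labelling error in a stated operating characteristic. At 10% on every count, with 20 participants for the safety counts, 0.867 is the most an arm can reach at the first full review. Plausible values are lower: about 0.65-0.78 for Arm B and 0.68-0.82 for Arms A and C, given the assumed dependence and rifabutin power of 0.90-0.94. These ranges are illustrations, not estimates or bounds. The all-arm figure is the least firm, because Arms A and C share control data and are not strictly independent.

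Two features could lower the true values further. Equivalence is required on Cmax as well as AUC, while Table 9.1 covers AUC only. Losses before day 28 count as failures in the safety analysis, but Table 9.2 is built on a toxicity rate alone; the documents give no loss rate and do not say which count a loss enters.

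**What to change.** 1. In Protocol 9.5.1, replace the sentence with: *If the underlying rate is 10%, a single count criterion is judged acceptable with probability 0.87 (X=3, n=20); the probability that an arm meets all of its criteria at the first full review is lower.* Add that dose adjustment and a second review may follow.
2. Give the joint probability for each arm and for all three arms, marked as illustration. The sponsor's statistician should compute it under stated assumptions on dependence between criteria, rifabutin power, PK-evaluable numbers and losses before day 28. PK-evaluable numbers should be handled consistently across arms. The values shown here should not be inserted as they stand.
3. In 9.4.1, state that the power above 90% refers to AUC alone, in one arm, at a true difference of about 5%; that Table 9.1 prints 90% at 10% and 52-70% at 20%; and that also requiring Cmax cannot raise it.

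The cost is one reworded sentence with a note, one short table and one clause. No threshold, sample size or procedure changes, and recruitment is unaffected. The stated probabilities become less favourable.

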#### 9.5.2 Overall Study Monitoring

Early deaths, defined as those occurring within the first two months on study, will be monitored by the core team. The cumulative number of deaths during the first two months on study will be combined across the treatment arms and will be calculated on a monthly basis using a Kaplan-Meier estimator and reported to the core team. Should more than 15% of the number of participants enrolled die during the first two months on study, the team will request that the NIAID DSMB review the study for safety. This review will include both safety data and efficacy data through week 48, as available.

After the final SMC review of the PK and safety data during the dose-finding period in accrual period 1 participants, this study will be reviewed at least annually by the NIAID Data Safety and Monitoring Board (DSMB). This DSMB will receive a copy of the full accrual period 1 PK and safety interim analysis. For all annual reviews, the DSMB will be provided detailed information on safety (including mortality and regimen tolerability) and administrative aspects (accrual, baseline characteristics of participants, compliance with specimen storage, and retention). The first safety review will take place approximately one year after the final SMC review. The first efficacy review will be timed to occur while enrollment is ongoing so any required changes to the protocol may be made before accrual ceases. Thus, the first efficacy review will take place when approximately 25% of all participants have completed 48 weeks of follow-up. The timing of the first efficacy review will be decided at the first safety review. Efficacy reviews will employ group sequential monitoring of survival probabilities with boundaries defined by the Haybittle-Peto rule, with repeated 99.995% confidence intervals on the difference in proportions with HIV RNA level < 400 copies/mL at 48 weeks (Arm B versus Arm A and Arm B versus Arm C). For monitoring efficacy, there are three scenarios with respect to the confidence intervals:

1. The lower bound of the CI is >0%
2. The CI includes 0%
3. The upper bound of the CI is <0%.

If the lower bound of the 99.995% CI on the difference is greater than 0%, then the experimental Arm (A or C) is superior to Arm B as hypothesized and the team intends for the study to continue to full accrual and follow-up. If the 99.995% CI on the difference includes 0%, then superiority has not been demonstrated (yet) and the team intends to evaluate this finding in conjunction with predicted interval

plots to evaluate the possibility of demonstrating superiority with trial continuation (e.g., evaluate futility) and the team intends for the study to continue to full accrual and follow-up since collecting secondary endpoints is desirable in this population regardless of possible futility. If the upper bound of the 99.995% CI on the difference is less than 0%, meaning Arm (A or C) is inferior, the team intends to evaluate this finding in the context of the toxicity and TB endpoints to determine whether the study or one of the treatment arms should be stopped while using predicted interval plots to evaluate the possibility of demonstrating superiority with trial continuation (e.g., evaluate futility).

The efficacy reviews will also include monitoring the TB cure rate. Since the team anticipates that Arm A will be non-inferior to Arm B and Arm C will be non-inferior to Arm B, there are two contrasts (Arm A vs. Arm B and Arm C vs. Arm B). A one-sided 97.5% CI for the difference in cure rates (i.e., A-B and C-B) will be calculated for each contrast and the lower bound of the interval will be compared to -10% (i.e., 10% is the non-inferiority margin). For interim monitoring of the TB cure rate, CIs for the difference in TB cure rates will be constructed as above. Again, there are three possible scenarios:

1. The lower bound of the CI is >0%
2. The lower bound of the CI is >-10% but <0%
3. The lower bound of the CI is <-10%.

If the lower bound of the CI is >0%, then the experimental arm (A or C) is superior to Arm B with respect to the TB cure rate and the team intends to evaluate this finding in the context of the HIV RNA and toxicity endpoints to determine whether the study should be stopped. If the lower bound of the CI is >-10% but <0%, then Arm A or C is non-inferior to Arm B and the team intends for the study to continue to full accrual and follow-up as designed. If the lower bound of the CI is <-10%, then non-inferiority has not been demonstrated (yet) and the team intends to evaluate this finding in conjunction with predicted interval plots to evaluate the likelihood of demonstrating non-inferiority with trial continuation (e.g., evaluate futility). The team discussed the possibility of a futility analysis and decided the study should continue to full accrual and follow-up as designed since collecting secondary endpoints is desirable in this population.

The number and timing of reviews will depend on the accrual rate and will be decided in conjunction with the DSMB.

Reports on adverse events pooled over arms, but summarized by accrual period, will be provided to the Division of AIDS Medical Officer every 6 months.

When approximately 25% of participants have completed 48 weeks of follow-up, overall sample size will be re-evaluated based on the current study rate of HIV virologic suppression in Arm B only. If the suppression rate is much higher than the hypothesized 50%, the protocol team will need to consider increasing the sample size in order to have sufficient power to detect smaller treatment differences (since the hypothesized 70% HIV virologic suppression in Arm A will

still hold). If the suppression rate is much lower than the hypothesized 50%, the protocol team discussed the possibility of doing a futility analysis but decided that collecting secondary endpoints is desirable in this population given that Arm B is standard of care in many resource-constrained settings. As the primary endpoint involves comparisons with Arm B, monitoring the Arm B (standard of care/control) rate alone will not affect the alpha level for the primary objective.

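### Section 9.5.2 appears to judge interim TB-cure superiority on an unadjusted one-sided 97.5% bound at every review and for two contrasts, and sends a crossing to a stopping discussion

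*Protocol*

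**What the plan says.** Protocol section 9.5.2 sets two different standards for the same efficacy reviews.

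- **HIV RNA.** Haybittle-Peto monitoring with repeated 99.995% intervals on the difference in the proportion below 400 copies/mL. If an experimental arm is superior, the team intends to carry on to full accrual and follow-up. If it is inferior, stopping the study or an arm is considered.
- **TB cure.** The section says "there are two contrasts (Arm A vs. Arm B and Arm C vs. Arm B") and that "A one-sided 97.5% CI for the difference in cure rates (i.e., A-B and C-B) will be calculated for each contrast", with the lower bound compared with -10%. It continues: "For interim monitoring of the TB cure rate, CIs for the difference in TB cure rates will be constructed as above". Three branches follow. The first reads: "If the lower bound of the CI is >0%, then the experimental arm (A or C) is superior to Arm B". The stated plan in that case is "to evaluate this finding in the context of the HIV RNA and toxicity endpoints to determine whether the study should be stopped".

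The section gives no TB-cure level that depends on the look, and no adjustment for two contrasts. On the schedule it says: "The number and timing of reviews will depend on the accrual rate and will be decided in conjunction with the DSMB". Only the first efficacy review is placed, at about 25% of participants with 48 weeks of follow-up. Section 9.6.3 adds that, apart from select virologic analyses reviewed by the DSMB, alpha for secondary analyses is not adjusted for multiple testing.

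**The concern.** The endpoint with the lower hurdle has the heavier consequence. Superiority on HIV RNA needs z of about 4.06 and leads to continuing. Superiority on TB cure needs z = 1.96, at any review and in either contrast, and opens a discussion of stopping. The protocol gives no reason for the difference.

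Two things are at stake. First, a chance crossing on a secondary endpoint could feed a decision to stop before the week-48 virologic question is answered. Second, an effect selected by an early crossing is overstated. With about 39 per arm (25% of 157), the observed difference must exceed roughly 1.96 × √(2 × 0.7 × 0.3 / 39) = 20 percentage points if cure is 70%, or 1.96 × √(2 × 0.9 × 0.1 / 39) = 13 points if it is 90%. Any early crossing would therefore look large even if the arms were equal.

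**Working it through.** **Inputs from the protocol.** One-sided 97.5% bound per contrast, superiority if the lower bound exceeds 0%, two contrasts sharing Arm B, and the first efficacy review at about 25% (9.5.2); 1:1:1 allocation (9.3); 157 per arm (9.4.2).

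**Assumptions.** Equal true cure rates of 60 to 90% (the documents give none), one to four looks, and the information fractions shown below.

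**The plan's own figure.** The protocol states no error rate for TB-cure monitoring. Its sample size, used here as the maximum per arm, reproduces. For 50% v 70%, two-sided 0.025 and 90% power, n = [2.241 × √(2 × 0.6 × 0.4) + 1.282 × √(0.25 + 0.21)]² / 0.20² = 146.7, so 147. Then 147 / 0.97 gives 152 and 152 / 0.97 gives 157.

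**Formula.** With no true difference, the chance of at least one false superiority label is 1 − P(all Z ≤ c). The Z values are jointly normal, with correlation √(t_i / t_j) between looks i < j of one contrast and 0.5 between contrasts at the same look; across contrast and look the two multiply. As a check, I simulated 200,000 binomial trials per setting with Wald bounds.

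**Results at c = 1.96, both contrasts.**

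| Looks (information fraction) | Normal theory | Binomial simulation |
|---|---|---|
| 1 (25%) | 4.5% | about 5 to 5.5% |
| 2 (25, 50%) | 7.4% | 8.2 to 8.5% |
| 2 (80, 100%) | 6.3% | 6.6 to 6.8% |
| 3 (25, 50, 75%) | 9.5% | 10.3 to 10.7% |
| 3 (80, 90, 100%) | 6.9% | 7.2 to 7.4% |
| 4 (25, 50, 75, 100%) | 11.0% | about 12% |

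For one contrast alone, normal theory gives 2.5%, 4.2%, 5.4% and 6.3% for one to four looks at the quarter points.

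**Why the high fractions belong in the table.** Cure is recorded at the end of TB treatment (6.3.7), which lasts at least 24 weeks (5.1.4), so it is known earlier than week-48 HIV RNA. Take even accrual of 411 participants over the planned nine months (9.4.3).

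- A quarter of 471 is 118, of whom 60 come from period 1. The other 58 are enrolled by month 58 / 411 × 9 = 1.3 of period 2 and reach week 48 (11 months) at about month 12.3.
- By then, everyone enrolled before month 12.3 − 5.5 = 6.8 has passed week 24. That is 60 + 411 × 6.8 / 9 = 371 of 471, or 79%.

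The fraction would be lower where treatment is extended towards 48 weeks.

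**Results at stricter bounds, three looks at 25, 50 and 75%, both contrasts.** At 99.995% (z = 4.06), about 0.013% by normal theory. At two-sided 99.9% (z = 3.29), about 0.25% by normal theory and at most 0.4% by simulation; it stays below 0.5% with a fourth look.

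**The case against.** **The cross-reference is ambiguous.** The sentence on interim intervals would be redundant if 97.5% were already the interim level, and 9.5.2 says efficacy reviews use Haybittle-Peto limits. It could therefore point back to 99.995%, with negligible risk. This is a fair reading, but the interval described immediately before is the one-sided 97.5% one, so that is the more natural reading. Either way the sentence needs an edit.

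**Three looks may never happen.** With reviews at least annual and a first efficacy review near month 12 of period 2, the next yearly one would fall at about month 24. That is after the last week-48 visit at about 9 + 11 = 20 months. One interim look, about 4.5 to 5.5%, is then realistic. This stands, and is why a range is given rather than a single 10%.

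**Stopping is not automatic.** This also stands. A reader might infer a 10% chance of wrongly ending the trial. The documents do not support that, because a crossing is weighed with HIV RNA and toxicity and no stopping probability can be derived.

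**Secondary analyses are declared unadjusted.** Section 9.6.3 describes those analyses as exploratory and hypothesis-generating. A rule that states superiority and feeds a stopping decision is a different use of the data, so that policy does not cover it.

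**The 0.025 per contrast may be a split of 5%.** The protocol does not say so, and a split would cover only a single look.

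**Conclusion.** The point holds on the natural reading of 9.5.2: interim TB-cure superiority has no protection against repeated looks or two contrasts, although its consequence is a discussion of stopping. With equal cure rates, the chance of at least one false superiority label is about 4.5 to 5.5% for one look, 6 to 8% for two and 7 to 10.5% for three. The spread reflects a schedule and information fractions that the protocol leaves open.

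Three stronger readings should be avoided. These percentages are not chances of a false stop. It is not true that only a TB-cure crossing can raise stopping: HIV inferiority does so too, and the contrast applies only to the two superiority branches. Nor do the documents show that the trial was affected. SAP section 1.6 says accrual period 2 will not open, so monitoring at 157 per arm will not take place and the point concerns the plan as written. The non-inferiority comparison with -10% is not criticised here.

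**What to change.** State in 9.5.2 that, at interim reviews, the TB-cure superiority branch (lower bound above 0%) uses the same Haybittle-Peto 99.995% interval as HIV RNA. If another level is preferred, give its sidedness and z value: a two-sided 99.9% interval is z = 3.29, and it keeps the total below about 0.5% for up to four looks.

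Keep the one-sided 97.5% bound for the comparison with -10%. State that interim non-inferiority readings are descriptive and that the formal conclusion is drawn at the final analysis. Because one interval now drives all three branches, each branch should name its level, and the phrase "CIs for the difference in TB cure rates will be constructed as above" should be replaced by that explicit statement.

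The cost is a few sentences in the monitoring section. Sample size and the primary analysis are unchanged. The downside is that early superiority on TB cure becomes harder to declare.
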